9.2 SETTING

The study will be conducted in a general practice setting, Korea National Health Insurance claim data & mortality data from the Bureau of Statistics, which includes computerized medical records of more than half million patients in South Korea. The maximal observation period will be from Jan 2005 to Apr 2016.

- Inclusion criteria
 - Diagnosed with COPD [**based on ICD-10 code(J43.x-44.x except J430), as the primary or within the fourth secondary diagnosis and initiated LAMA or ICS/LABA more than twice a year from Jan 1, 2005 to Apr 30 2016**].
 - Age >55 years old as of 2005 when enroll started
- Exclusion criteria
 - Prescription history with any long acting bronchodilator for maintenance therapy (the patient should be inhaler naïve) from 2002 to 2005.
 - Prescription history with ipratropium bromide
 - Prescription history with Leukotriene receptor antagonist(LTRA) or ICS
 - Prescription history of LABA/LAMA FDC
 - Patients with lung cancer, IPF, ILD or lung transplantation at the time of COPD diagnosis

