9.3.2 Outcomes

9.3.2.1 Primary outcomes

Primary endpoint

- Recorded pneumonia based on 1)ICD-10 code (J12.x-J18.x, J69.0, J84.9, B96.0, J85.1) AND 2) CPT code of chest x-ray(71045-71048) or chest CT(71250,71260,71270,G0297) AND 3) prescription of antibiotics for pneumonia in Korean Guideline) incidence rate per year
- Frequency rate of COPD exacerbation per year
 - Moderate exacerbation: recorded as when COPD patients visited outpatient clinics with an ICD-10 code of COPD and systemic steroid medication and/or antibiotics were prescribed (within the first year after initial prescription of inhalers)
 - Severe exacerbation: when COPD patients visited the emergency room or were admitted to hospital with an ICD-10 code of COPD(*due to COPD worsening*) and were prescribed systemic steroid medication and/or antibiotics (within the first year after initial prescription of inhalers)
- Time to start triple combination therapy ICS/LABA/LAMA)
 - Time to add LAMA in patients with using ICS/LABA or, time to add ICS/LABA in patients with using LAMA before.

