ANNEX 3. ADDITIONAL INFORMATION

Appendix Table 1. List of variables in the NHIS database

DB (number of variables)	Variable name	Details
The eligibility of the insured DB	STND_Y	Standard year for the eligibility of the insured
	PERSON_ID	Personal identification number is replaced by serial number
	SEX	Sex
	AGE_GROUP	Age group at time of diagnosed
	DTH_YM	Year and month of death
	DTH_CODE1	Level 1 (detailed) cause of death
	DTH_CODE2	Level 2 cause of death
	SIDO	Province of residence
	SGG	District of residence
	CTRB_PT_TYPE_CD	Percentile group of income level
The medical treatment DB (called Table 20) [electronic bill of medical treatment]	PERSON_ID	Personal identification number is replaced by serial number
	KEY_SEQ	Key sequence number of claim
	YKIHO_ID	Medical care institution identification number
	RECU_FR_DT	The first day of receiving treatment
	FORM_CD	Form of claimed bill
	DSBJT_CD	Medical subject code
	MAIN_SICK	Main disease code
	SUB_SICK	Sub disease code
	IN_PAT_CORS_TYPE	Route through hospitalization
	OFFC_INJ_TYPE	Type of injuries incurred while on duty

DB (number of variables)	Variable name	Details
	RECN	Days of receiving medical care
	VSCN	Days of visit hospitals or inpatient
	FST_IN_PAT_DT	First date of inpatient
	DMD_TRAMT	Amount of medical expenses based on claims
	DMD_SBRDN_AMT	Expenses paid by beneficiary based on claims
	DMD_JBRDN_AMT	Expenses paid by insurer based on claims
	DMD_CT_TOT_AMT	Total amount for CT based on claims
	DMD_MRI_TOT_AMT	Total amount for MRI based on claims
	EDEC_ADD_RT	Extra rate applied based on claims reviewed
	EDEC_TRAMT	Amount of medical expenses based on claims reviewed
	EDEC_SBRDN_AMT	Amount of expenses paid by beneficiary based on claims reviewed
	EDEC_JBRDN_AMT	Amount of expenses paid by insurer based on claims reviewed
	EDEC_CT_TOT_AMT	Total amount for CT based on claims reviewed
	EDEC_MRI_TOT_AMT	Total amount for MRI based on claims reviewed
	DMD_DRG_NO	DRG number of claim
	MPRSC_ISSUE_ADMIN_ID MPRSC_GRANT_NO	Institution identification number which issued prescriptions Prescription identification number (newly added since 2011 database)
	TOT_PRES_DD_CNT	Total days of prescription
	KEY_SEQ	Key sequence number of claim

DB (number of variables)	Variable name	Details
The medical treatment DB (called Table 30) [details of medical treatment bill]	SEQ_NO	Sequence number
	RECU_FR_DT	Date of the first treatment
	CLAUSE_CD	Code for clause
	ITEM_CD	Code for item
	DIV_TYPE_CD	Code for the type of treatment

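### A first-year pneumonia visit that also carries a COPD code can count in two primary endpoints, which tilts the exacerbation comparison against ICS/LABA if ICS raises pneumonia

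*Combined protocol and SAP*

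**What the plan says.** Section 9.3.2.1 of the protocol lists pneumonia and COPD exacerbation as separate primary endpoints.

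- **Moderate exacerbation:** an outpatient visit "with an ICD-10 code of COPD and systemic steroid medication and/or antibiotics were prescribed".
- **Severe exacerbation:** an emergency room visit or admission with a COPD code, qualified by "due to COPD worsening", for patients who attended "and were prescribed systemic steroid medication and/or antibiotics (within the first year after initial prescription of inhalers".
- **Pneumonia:** a code from the list "ICD-10 code (J12.x-J18.x, J69.0, J84.9, B96.0, J85.1", plus chest imaging, plus "prescription of antibiotics for pneumonia in Korean Guideline".

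Both kinds of exacerbation are counted only "within the first year after initial prescription of inhalers". Neither says which diagnosis position the COPD code must hold. For cohort entry, section 9.2 accepts COPD "as the primary or within the fourth secondary diagnosis". Section 9.7.2 analyses each primary outcome separately, follows patients for up to 11 years, and gives no rule for an event that meets two definitions. Appendix Table 1 includes MAIN_SICK ("Main disease code") and a sub disease code, but no variable that records worsening of COPD.

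**The concern.** The drug criterion for an exacerbation is already met by every qualifying pneumonia, because the pneumonia endpoint requires antibiotics. Every patient in the cohort has COPD. The one further condition for double counting at an outpatient visit is that the claim also lists COPD.

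Section 8 says that long-term ICS use is reported to increase serious pneumonia. If that holds here, pneumonia events that spill into the exacerbation count are more frequent on ICS/LABA. The exacerbation comparison then shows a disadvantage for ICS/LABA that is partly the pneumonia result counted again. A reader would take the two endpoints as separate evidence on harm and on effectiveness, and to that extent they would not be.

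**Working it through.** **Step 1. Definitions side by side (section 9.3.2.1)**

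| Element | Moderate exacerbation | Severe exacerbation | Pneumonia |
|---|---|---|---|
| Setting | Outpatient | ER or admission | Not restricted |
| Code | COPD, position not stated | COPD, position not stated, with a worsening qualifier | Pneumonia list; a COPD code does not exclude |
| Antibiotics | Sufficient alone | Sufficient alone | Required |
| Excludes the other endpoint | No | Only by the intent of the qualifier | No |

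An outpatient pneumonia in the first year with COPD also coded satisfies the first and third columns.

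**Step 2. Formula**

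The plan gives no event rates, effect size, alpha or power for these endpoints, so there is no figure to reproduce. The 5,000 per arm in section 9.5 is a feasibility minimum. If exacerbations truly do not differ, the observed rate ratio (ICS/LABA over LAMA) is

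RR = (e + f·p·h) / (e + f·p)

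where e = genuine exacerbations per patient-year, p = pneumonia rate on LAMA, h = pneumonia rate ratio, and f = share of pneumonias that carry a COPD code and are not already genuine exacerbations. **All four are assumptions.** RR exceeds 1 whenever h > 1 and f·p > 0, so the direction is fixed and only the size is open.

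**Step 3. Rate ratio and chance of p < 0.05**

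This uses 5,000 per arm, one year, a two-sided Wald test on log RR with SE = √(φ(1/events₀ + 1/events₁)), and ignores matching. φ is the overdispersion.

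| Case | e, p, f, h | Events, LAMA vs ICS/LABA | RR | p < 0.05, φ = 1 | φ = 2 |
|---|---|---|---|---|---|
| All, low | 0.6, 0.05, 0.5, 1.3 | 3,125 vs 3,162.5 | 1.012 | 8% | 6% |
| All, mid | 0.6, 0.06, 0.5, 1.5 | 3,150 vs 3,225 | 1.024 | 16% | 10% |
| All, full overlap | 0.6, 0.05, 1, 1.5 | 3,250 vs 3,375 | 1.038 | 34% | 19% |
| All, high | 0.3, 0.05, 1, 1.7 | 1,750 vs 1,925 | 1.10 | 82% | 53% |
| Severe, low | 0.10, 0.03, 0.5, 1.3 | 575 vs 597.5 | 1.039 | 10% | 8% |
| Severe, mid | 0.10, 0.03, 1, 1.5 | 650 vs 725 | 1.115 | 52% | 30% |
| Severe, high | 0.06, 0.03, 1, 1.7 | 450 vs 555 | 1.233 | 91% | 65% |

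Example, severe mid: ln(725/650) = 0.109; SE = √(1/650 + 1/725) = 0.054; z = 2.02. The severe rows apply only if the worsening qualifier is not enforced. A wider grid (e 0.3 to 1.0, p 0.03 to 0.10, h 1.2 to 2.0, f 0.25 to 0.9) gives RR 1.002 to 1.23.

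**Step 4. The opposite error**

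Dropping every pneumonia-coded episode also removes genuine exacerbations that occur with pneumonia. If a share c of pneumonias are such episodes, RR = (e − c·p·h)/(e − c·p). With e = 0.6, p = 0.06, h = 1.5 and c = 0.5 (assumed), this is (0.6 − 0.045)/(0.6 − 0.03) = 0.555/0.570 = 0.974. On the same e, p and h, the broad count with f = 0.5 gives 1.024. The two versions fall on either side of the true value of 1.

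**The case against.** Four stronger readings are tempting, and the documents do not support them.

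- **Severe events plainly include pneumonia admissions.** The worsening qualifier, on its face, points away from an admission caused by pneumonia. What is missing is a claims rule that applies it. The largest ratios above therefore depend on the qualifier being ignored.
- **Every qualifying claim is an event.** The section speaks of patients who visited or were admitted and gives no counting rule. Appendix Table 1 lists admission route, first inpatient date and treatment dates, which could link an ER visit to an admission. Episode construction is unstated; it is not wrongly stated.
- **The plan never deals with overlap.** Sections 9.3 and 9.7 defer detail to an SAP. The contents list has a redacted entry after 9.7.2, and the ENCePP checklist cites a section 9.7.3 for outcome validity, information bias and sensitivity analyses. Relevant analyses may be there. They would not change the visible primary definition, and section 9.7 says that major modifications of primary endpoint definitions would be reflected in an amendment.
- **The exacerbation result will be falsely significant.** Most low and middle cases would not reach significance.

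Two further limits stand. Exacerbations are counted in the first year only, so most of the pneumonia follow-up cannot overlap. Section 8 links pneumonia to long-term ICS use, so applying a raised ratio to year one is itself an assumption. It is also fair to say that excluding all pneumonia-coded episodes would bring a bias of its own, in favour of ICS/LABA.

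**Conclusion.** The point holds in limited form. For moderate events, the visible definition lets one first-year visit count in two primary endpoints. For severe events, the limiting phrase has no rule that a programmer could apply. If ICS/LABA raises pneumonia within the first year and some pneumonia claims carry a COPD code, the bias runs against ICS/LABA.

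Its size is unknown. The assumed inputs give about 1.01 to 1.10 for all exacerbations and up to about 1.23 for severe events with the qualifier not applied. A false finding with 5,000 per arm becomes likely only towards the upper end of those ranges. Because 5,000 is a minimum, a larger cohort would make a small bias easier to mistake for an effect. Confidence is medium, because the overlap follows from the text and its magnitude does not.

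**What to change.** Amend section 9.3.2.1 before analysis:

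1. For severe events, require COPD as MAIN_SICK, so that the worsening qualifier becomes a claims rule.
2. For moderate events, state which diagnosis positions the COPD code may hold.
3. Define an episode: link an ER visit to the admission that follows, and join visits within a fixed gap (14 days, for example).
4. Report the exacerbation comparison twice, with and without episodes that meet the pneumonia algorithm. Claim an exacerbation benefit separate from pneumonia only if both versions agree.

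**Cost.** The variables are already in Appendix Table 1, so the programming is modest. The change needs a protocol amendment, and section 9.8 requires approval by the principal investigator, the co-investigators and the sponsors. A main-diagnosis rule may be strict and lose some true events. The version without pneumonia episodes drops genuine exacerbations with pneumonia, which favours ICS/LABA, so the two versions should be read as a range. If the SAP or the redacted text already holds such an analysis, 9.3.2.1 should refer to it.

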9.7.2 Main analysis

For the primary effectiveness outcomes incidence rates (events per 1,000patients-years) with corresponding 95% confidence intervals (CI) will be calculated. This will be evaluated by a matched Cox proportional hazards regression model for counting processes, which allow the follow-up time to be divided into several periods and therefore control for baseline and time-dependent covariates, using the full observational period of available data, i.e. up to 11 years of follow up. The Cox proportional hazards regression will take into account the fact that individual matching (1:1) will be performed by considering the exposed patient and his/her matched controls as one stratum and including this as a stratum in the Cox proportional hazards model. Additional variables will be included in the model if available. The cumulative incidence plots will be accompanied by number of patients at risk at different time points during follow-up. For (possibly) repeating events (such as exacerbation event) additionally a Poisson regression model will be fitted for the number of events (taking into account the matching). Time in the study will be included as an offset variable in the model. The cox and Poisson models will be adjusted for unbalanced PS-variables at baseline.

The outcome will be analyzed separately for each:

- 1) Primary outcome
 - Comparison of pneumonia incidence in COPD patients using LAMA and ICS/LABA
 - Comparison of exacerbations frequency and rate in COPD patients using LAMA and ICS/LABA : moderate or severe exacerbation

Proprietary confidential information © 2022 Boehringer Ingelheim International GmbH or one or more of its affiliated companies

[figure not shown]
- Comparison of time to start triple combination therapy (time from initial 'LAMA mono' or ICS+LABA' to 'LAMA+LABA+ICS' combination) in COPD patients using LAMA and ICS/LABA

2) Secondary outcome

- Comparison of all-cause mortality differences in COPD patients using LAMA and ICS/LABA
- Comparison of lung cancer incidence in COPD patients using LAMA and ICS/LABA
- Comparison of health care utilization: Medical cost / No. of prescriptions, visits and hospitalizations (hospitalization mainly due to severe exacerbation of COPD)

Health care utilization

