9.12 BIAS

This study will include users of LAMA and ICS/LABA. Immortal time bias will be minimal, as the follow-up will begin at the initiation of drug use. Adherence to drug use will be unknown.

Comparing the outcomes between users of LAMA and ICS/LABA will decrease confounding by indication, as the comparison group will have a similar indication to drug use than the patients in the LAMA-exposed cohorts.

The compared sub-cohorts will be matched on the basis of PS. The PS will be computed on the basis of a wide range of covariates related to sociodemographic characteristics, history of exacerbation, other comorbidities, and prior/concomitant use of other drugs. The PS matching will decrease the systematic differences between the sub-cohorts and, thus, decrease confounding.

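### Time zero is the first inhaler prescription, with no readable rule for day 0 or for an episode already under way, so claims from the pneumonia or exacerbation that prompted the inhaler can be counted as outcomes

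*Combined protocol and SAP*

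**What the plan says.** **Start of follow-up.** Section 9.12 states: "Immortal time bias will be minimal, as the follow-up will begin at the initiation of drug use". This is the only statement of time zero that covers all outcomes.

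**Exacerbations (9.3.2.1).** A moderate event is an outpatient visit with a COPD code at which "systemic steroid medication and/or antibiotics were prescribed (within the first year after initial prescription of inhalers". A severe event uses the same drugs and the same one-year window, but needs an emergency visit or an admission.

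**Pneumonia (9.3.2.1).** The definition combines a diagnosis code, chest imaging and antibiotics, and ends "prescription of antibiotics for pneumonia in Korean Guideline) incidence rate per year". It gives no start day, no prior-event rule and no rule for telling a new episode from a continuing one.

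**Follow-up length (9.7.2).** The primary outcomes are modelled "using the full observational period of available data, i.e. up to 11 years of follow up".

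**Eligibility (9.2).** The washouts concern drugs, for example "Prescription history with any long acting bronchodilator for maintenance therapy (the patient should be inhaler naïve) from 2002 to 2005". The disease exclusion is "Patients with lung cancer, IPF, ILD or lung transplantation at the time of COPD diagnosis". Recent pneumonia or exacerbation is not mentioned.

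**Confounder control (9.3.3, 9.7.1.1).** Exacerbation history is a matching and propensity-score variable, with no look-back period given. Pneumonia history is not listed.

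**Dates (Appendix Table 1).** The main claim table dates a record by RECU_FR_DT, described as "The first day of receiving treatment". The detail and prescription tables carry the same variable.

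**The concern.** Take an inhaler-naive patient who attends with worsening COPD or pneumonia, receives an antibiotic or a systemic steroid, and gets a first LAMA or ICS/LABA within the same episode. Cohort entry needs a COPD code and the inhaler. A moderate exacerbation needs an outpatient visit with a COPD code and a steroid or an antibiotic. One visit can satisfy both. A repeat visit some days later, with treatment continued, can satisfy the exacerbation rule again. For pneumonia, follow-up imaging and a further antibiotic can satisfy all three elements of the definition.

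Such an episode began before the drug and cannot be an effect of it. Counting it adds the same kind of noise to both arms if acute starts are equally frequent, and this pulls a real difference towards 1. If one class is started in acute episodes more often, the comparison partly reflects why the drug was prescribed. Pneumonia is the more exposed outcome, because prior pneumonia is not named among the exclusions or the propensity-score variables.

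**Working it through.** **What can be reproduced.** The only size figure in the plan is at least 5,000 per arm: 2 × 5,000 = 10,000, which agrees with the stated total. The plan gives no event rate, effect size, alpha or power, and no share of patients who start an inhaler during an acute episode. Every input below other than 5,000 per arm is an assumption, chosen to show a range.

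**Formula.** Let λ be the true yearly event rate in the LAMA arm, RR the true rate ratio (ICS/LABA to LAMA), T the years of follow-up, and c0 and c1 the shares of LAMA and ICS/LABA patients whose index episode is counted. Then

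observed ratio = (RR·λ·T + c1) / (λ·T + c0).

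**Pneumonia, true RR 1.5, equal carry-over (c0 = c1 = c)**

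| λ | c | First year | Five years |
|---|---|---|---|
| 0.03 | 1% | 0.055/0.040 = 1.38 | 0.235/0.160 = 1.47 |
| 0.03 | 5% | 0.095/0.080 = 1.19 | 0.275/0.200 = 1.38 |
| 0.06 | 1% | 0.100/0.070 = 1.43 | 0.460/0.310 = 1.48 |
| 0.06 | 5% | 0.140/0.110 = 1.27 | 0.500/0.350 = 1.43 |

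With rates of 75 and 50 per 1,000 and only 0.5% carry-over in each arm, the first-year ratio is 80/55 = 1.45, so the dilution is small.

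**Pneumonia, true RR 1.0, unequal carry-over (c0 = 2%)**

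| λ | c1 | First year | Five years |
|---|---|---|---|
| 0.03 | 4% | 0.070/0.050 = 1.40 | 0.190/0.170 = 1.12 |
| 0.03 | 1% | 0.040/0.050 = 0.80 | 0.160/0.170 = 0.94 |
| 0.06 | 4% | 0.100/0.080 = 1.25 | 0.340/0.320 = 1.06 |
| 0.06 | 1% | 0.070/0.080 = 0.88 | 0.310/0.320 = 0.97 |

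The chance of a false-positive first-year difference can be approximated by comparing two proportions, 1 − (1 − c)·exp(−λ), at 5,000 per arm. With 2% against 4% it is about 98% for λ = 0.03 and 92% for λ = 0.06. With 2% against 3% it is about 57% and 41%. The planned analysis is a matched Cox model, so these figures are indicative only.

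**Exacerbations, one-year window**

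- True RR 1.2, equal carry-over of 10% to 30%: for λ = 0.5, 0.70/0.60 = 1.17 to 0.90/0.80 = 1.13; for λ = 1.0, 1.30/1.10 = 1.18 to 1.50/1.30 = 1.15.
- True RR 1.0, λ = 0.5: 10% LAMA against 20% ICS/LABA gives 0.70/0.60 = 1.17; 20% against 10% gives 0.60/0.70 = 0.86.
- True RR 1.0, λ = 1.0: the same two cases give 1.20/1.10 = 1.09 and 1.10/1.20 = 0.92.

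The unequal exacerbation cases allow nothing for matching on exacerbation history, so they are upper-end illustrations.

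**Effect of a rule.** If index episodes are set aside, c0 = c1 = 0 and the formula returns the true ratio. A 14-day lag removes 14/365 = 3.8% of a one-year window under constant risk.

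**The case against.** The strongest reply is that the exacerbation window is worded as running after the initial prescription, so on a strict reading the prompting episode falls outside it. That stands against the inference that the prompting episode is always counted. It leaves open who owns day 0, and it does not stop later claims of the same episode from counting. For pneumonia there is no such wording, and only the start of follow-up in 9.12 applies.

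Second, a rule may exist where it cannot be read. Sections 9.3 and 9.7 defer detail to a SAP that is not supplied, and the ENCePP checklist cites section 9.7.3, which is not visible, for time-related bias and sensitivity analyses. It would therefore be wrong to conclude that the plan as a whole lacks a rule. However, section 9.7 itself says that major changes to primary endpoint definitions go into a protocol amendment, and which events count belongs to that definition.

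Third, exacerbation history is matched on, and imbalance is adjusted for. This may narrow a difference in carry-over between the arms, but it does not take the carried-over events out of the count. Section 9.12 also speaks broadly of other comorbidities in the propensity score, yet the list in 9.7.1.1 does not name pneumonia.

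Fourth, a reader might infer from RECU_FR_DT that the data cannot separate drug from event. The dates are coarse, and an inhaler given late in an admission can share the admission's date. But Appendix Table 1 also lists FST_IN_PAT_DT, RECN and VSCN, so an index admission can be identified and set aside.

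Finally, a reader might take the first year as the only window for exacerbations. Section 9.3.2.1 points that way, but 9.7.2 models the primary outcomes over up to 11 years; the two need reconciling. Over longer follow-up the distortion is smaller.

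**Conclusion.** The point holds as an open time-zero rule. As the readable text stands, same-day or continuing claims from the episode that prompted the inhaler can be counted as outcomes, for pneumonia and for exacerbations.

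Neither size nor direction can be fixed from the documents, and nothing in them shows which class is started more often in acute episodes. Under the assumed ranges:

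- Equal carry-over moves a first-year pneumonia ratio of 1.50 to 1.19–1.43, and a five-year ratio to 1.38–1.48.
- Unequal carry-over turns a null pneumonia ratio into 0.80–1.40 in the first year and 0.94–1.12 over five years.
- For exacerbations in a one-year window, a true 1.20 becomes 1.13–1.18, and a null becomes 0.86–1.17.

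If acute starts are rare, the effect is minor. The conclusion rests on the visible text only and would fall away if the SAP or section 9.7.3 contains a rule. The statement in 9.12 about immortal time does not settle it, because that is a different bias.

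**What to change.** Unless the SAP or section 9.7.3 already does so, amend sections 9.3.2.1 and 9.12, with a matching change to 9.7.1.1:

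1. State who owns day 0. Treat any pneumonia or exacerbation episode that includes or overlaps the index claim or index admission as baseline history, never as an outcome. Identify index admissions with FST_IN_PAT_DT, RECN and VSCN.
2. Count outcomes and person-time from the same prespecified short lag in both arms, for example 14 days after the index date or index discharge. The length is an analytic choice; it does not come from the documents.
3. Define a minimum gap between episodes for both outcomes.
4. Give the look-back period for exacerbation history, and add recent pneumonia history to the propensity score.
5. Report the day-1 start as a sensitivity analysis.
6. Reconcile the one-year exacerbation window in 9.3.2.1 with the follow-up in 9.7.2.

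**Cost.** A short amendment, plus programming of time zero and of the Poisson offset. Genuine early events are lost: about 4% of a one-year window for a 14-day lag under constant risk, and somewhat more for patients admitted at index.
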